7. Practical and ethical considerations for Component C: Peer education

It is essential that participants conducting peer education with their peers provide accurate and up-to-date information, are not coercive, and that peers understand the nature of the interaction and what is expected of them. We are highly experienced in interventions that entail peer-to-peer education. Peer education will be carried out by participants using a set of core messages. Participants will be trained by research study staff on when, where, and how to educate peers. Participants will be provided with a handout that guide the interaction with peers.

Participants will be walked through a discussion of how to carry out peer education in a way that minimizes risk of exposure to COVID including conducting education virtually, outdoors, and the use of safety precautions such as masks.

Participants will be trained to understand that peers should not be pressured or coerced into receiving peer education or contacting the research study. In the training, participants will be instructed on:

1. WHO to approach: Persons who you know by name or face and have seen in the past 30 days. These peers should be aged 18 and older, and should not already be enrolled in the NCAP study. To maximize the benefits of this study, we recommend you educate frontline essential workers from African American or Black or Latino racial/ethnic backgrounds.

2. WHEN to approach: at a time that mutually convenient and that does not disrupt work or other activities

3. Where peer education should take place: in a confidential and private location

4. How to avoid COVID-19 risk during peer education: adhere to public health prevention guidelines such as masking and social distancing or conduct peer education virtually

5. What the participant should do, step-by-step:

- **Ask-** Ask for some time with the peer.
- **Find –** Find a private location (or carry out the encounter virtually)
- **Explain –** Explain the main parts of what you want to say:
 - I am part of a research project called the NCAP Project
 - The goal of the NCAP Project is to bring information about COVID-19 testing to the community.
 - Today I will share some information I have been learning about COVID testing and treatment and ask you if you are willing to contact the NCAP study to do a brief interview.
 - You can tell me if you do not wish to have a discussion today and you can decline to call the NCAP study to do the interview.
- **Educate –** Educate Peer On the Core Messages (found in Table 3 and on the handout)
- **Give –** Give peer the Core Messages wallet card. (This card will have the core messages and the study phone number)
- **GIVE –** referrals to COVID-19 testing sites if needed (handout)
- **Explain next steps –** Explain the following:

- NCAP is a research project to learn more about what people think about COVID-19 testing and the best ways to support COVID-19 testing in the community
- If you call NCAP, you would do a short interview on the phone or in-person. The interview includes some true/false questions on these Core Messages.
- Peers would get \$25 for the interview.
- OPTIONAL – I will also get some compensation if you do the interview.
- Provide peer with the coupon.

Participants will be trained in talking tips:

- **Pick a good time.** Make sure the person is not busy. Ask if you could take up 5-10 minutes of their time to discuss something.
- **Pick a good place.** A place that is confidential and comfortable.
- **Stay neutral.** Keep your voice calm and pleasant. Remember, that you are only offering to provide them with information. They have a right to not be interested or not want to listen.
- **Watch your body language.** The messages you send with your body are as important as what you are saying to them. This is especially true if the peer you are educating is not very receptive.
- **Reflect and validate what they say...even if you disagree.** Validating their opinions and what they say even if you disagree with them helps to diffuse any tension. Using words such as “I hear you” or “I think I understand what you are saying (e.g., that you don’t believe that COVID-19 testing is right for you, etc.).

8. The importance of medical accuracy of materials

All materials and all information provided to the participants on COVID-19, COVID-19 testing, and vaccination will be reviewed regularly by our team medical expert to ensure that they are accurate and up-to-date (e.g., reviewing CDC and NYC Health information regularly and updating the information as needed). This includes the core messages for Component C (peer education).

[figure not shown]
9. Description of the factorial design and figure

A factorial experiment testing four intervention components, each with two levels, is comprised of 16 conditions (2^4 , see Fig. 2). Importantly, the design is not a 16-arm RCT. Factorial experiments separate component effects, enabling estimation of the main effect contribution of each component. Factorial experiments can be economical compared to alternative designs, because they require substantially fewer participants to achieve the same goals⁴⁸. For example, conducting four individual experiments using the RCT design, one for each component, would require $N=1792$ (448 participants per trial). Thus, the purpose and logical underpinnings of the factorial experiment are different from those of an RCT. The purpose of an RCT is a direct comparison of the efficacy of two or more versions of an intervention. By contrast, a factorial design never calls for a direct comparison of experimental conditions to see which one is best. Instead, the purpose is to identify which components show effectiveness. Efficiency comes from basing all estimated main effects on all 16 conditions in the factorial experiment. For example, the main effect of Component C will be estimated by comparing the mean outcome across Conditions 1-8 vs. across Conditions 9-16. All participants are included in the estimate of each main effect. Factorial experiments can have a small per-condition N ($N=28$) and still achieve study aims if the total N ($N=448$) is sufficient. All participants receive the core intervention, two conditions (15 & 16)

receive 1 component (access, either navigation or a self-test kit), 2 conditions (1 & 2) receive all components, and the remaining 12 conditions receive 2-3 components (Fig. 2).

Figure 2. Factorial Design Conditions

No	○	Navigation	△
Yes	●	Self-Test Kit	▲

10. Compliance Statement

This study will be conducted in full accordance all applicable Policies and Procedures of the UCAIHS at NYU and all applicable Federal and state laws and regulations including 45 CFR 46. All episodes of noncompliance will be documented.

The investigators will perform the study in accordance with this protocol, will obtain consent and assent, and will report unanticipated problems involving risks to subjects or others in accordance with UCAIHS and all federal requirements. Collection, recording, and reporting of data will be accurate and will ensure the privacy, health, and welfare of research subjects during and after the study.

11. Study Objectives

11.1. Primary aims

11.1.1. Aim 1

Aim 1. Identify which of four components contribute meaningfully to improvement in the primary outcome, COVID-19 testing with documentary evidence, and from these results, optimize an efficient multicomponent intervention. Participants will be English and Spanish-speaking BLH-FEW (ages 18-70 years; N=448) in New York City who have not been tested for COVID-19 in the past six months and who are not vaccinated for COVID-19. Participants will be randomly assigned to an intervention condition, engage in the assigned components, and assessed at 6- and 12-weeks post-baseline.

11.1.2. Aim 2

Aim 2. Identify mediators (e.g., distrust, altruism, access) and moderators (e.g., sociodemographic characteristics) of the effects of each component to better understand the intervention components' mechanisms of action and conditions under which they are most effective to advance future research and inform implementation of the optimized intervention.

11.1.3. Aim 3

Aim 3. Explore the relationships among barriers to, facilitators of, and uptake of COVID-19 testing and COVID-19 vaccination. In qualitative research we will explore participants' experiences with and perspectives on the intervention components and on COVID-19 testing and vaccination ($N=50$) and integrate qualitative and quantitative results using the joint display method to inform intervention implementation and future research.

12. Investigational Plan

12.1. General schema of study design

The study design is presented in Figure 1 above.

12.2. Refinement phase/pilot study

We will carry out additional refinements of the components in this first phase of the study. We anticipate these to be minor (e.g., wording and length of exercises). To do so, we will form an intervention working group (IWG) led by [name] and comprised of the project coordinator at NMIC, the CAB, and Drs. [name], [name], [name] and senior project staff members. We will also form a community advisory board. We will carry out an initial review of materials and then carry out a pilot study with members of the target population. Participants will engage in the pilot test virtually or in-person. Participants may engage in more than one 2.5 hour meeting depending on their interest and availability.

Procedures for the pilot study in the refinement phase are as follows:

- Potential participants will be recruited using the hybrid method described in this protocol (see below)
- Verbal consent will be obtained for screening
- They will be screened for eligibility using a structured instrument
- Consent will be obtained for enrollment in the pilot study (signed consent if in-person or verbally if virtual contact)
- Locator form completed
- Intervention session comprised of a subset of intervention components and a cognitive interview lasting approximately 2.5 hours in-person, over Zoom, or in the phone
 - All participants will receive the core session
 - Participants will be asked to engage in two of the following: 1) one **counseling session** (lasting about 30-45 minutes) with a study counselor to discuss your health decisions, and discuss what you think about COVID testing; 2) **receiving text messages** over 3 weeks (2 messages a week) with information about COVID and COVID-19 testing, along with quiz questions for which you earn 10 points for a correct answer and 5 points for an incorrect answer and compensation based on total points (max. points is 60); 3) training on **peer education** (15-20 minutes), where you will be trained to educate peers on core messages about the importance of COVID-19 testing, and you will be given the opportunity to educate three Black and Latino/Hispanic peers on these core messages, and

- Also, participants will be randomly assigned (by a coin flip) to receive **navigation** guidance to assist them in accessing COVID-19 testing OR **FlowFlex rapid COVID test kits**, along with instructions on conducting the test and interpreting results.
- Some participants will have the opportunity to educate up to 3 peers. Peers will contact the study directly and receive a brief assessment.
- Some participants will receive the TMQQs for 3 weeks after the initial meeting
- A subset will receive an open-ended follow-up interview lasting < 60 minutes to review experiences with components and solicit perspectives on improving components. This will not be audio-recorded but notes will be taken.

Sample size for refinement phase/pilot study: We will test the components with approximately $N=30$ participants (6 participants for each component and the core session minimum) and up to 50 participants as needed, since some components may need more pilot testing and refinement than others.

Structure of the pilot study: The pilot study will be structured as a single meeting with participants lasting approximately 2.5 hours. In this meeting, participants will receive the core session, 2 components from among Components A, B, and C, and Component D (with level of component D decided by a coin toss). Participants will receive the component and be asked to reflect on the clarity, acceptability, and utility of each major section of the component (the cognitive interview).

Eligibility for the refinement phase: Eligibility criteria will be similar to the larger trial.

1. age 18-70 years
2. can engage in study activities in English
3. Black or African American (including Caribbean, African, or multi-ethnic Black) and/or Latino or Hispanic race/ethnicity
4. resides in NYC
5. in the past month, was employed as a frontline worker in the occupations listed in this protocol
6. has a phone that can be used for study participation and can receive text messages
7. is not “fully vaccinated” for COVID-19
8. has not been tested for COVID-19 in the past six months
9. if previously diagnosed with COVID-19, has not been symptomatic in the past two weeks or 90 days has passed since treatment with monoclonal antibodies or convalescent plasma⁹⁸
10. willing to be assigned to one or more intervention components

Recruitment procedures for the refinement phase: These will be the same as recruitment procedures described for the larger trial.

Each pilot test session includes an in-depth qualitative cognitive interview⁵¹ and an assessment of acceptability. Cognitive interviewing is a psychologically oriented method for empirically studying the ways in which individuals process and respond to survey questionnaires and intervention content⁵¹ (e.g., critique of each core message or TMQQ). The feedback and acceptability ratings, along with feasibility ratings, will be brought to the IWG for discussion and recommendations for refinement. If the intervention is not adequately refined at this point it will undergo another round of pilot testing.

Peers in Component C: In addition, as part of Component C, 18 peers will be educated by study participants, will contact the study themselves, and will be assessed to evaluate Component C. This assessment will include brief semi-structured questions to explore the peer education process.

Follow-up interview: In some cases, participants will be contacted for an unstructured, qualitative follow-up interview, including dates and types of COVID-19 testing and/or vaccination (showing test results or certificates where appropriate). The interview will take place within one month of the first

component test meeting. They will be asked to reflect back on the component and ways it was helpful and ways it could be improved.

Goals of the refinement phase: At the conclusion of this phase, the intervention component protocols and study procedures will be complete, and assessments will be programmed in REDCap. Materials will be translated into Spanish. The activities in this phase are feasible: We will modify an existing REDCap database for a MOST study, and have already drafted and tested intervention component manuals.

12.3. Study duration, enrollment and number of sites

This is a 2-year study. There is one performance site (NYU). Study activities will be carried out by NYU study staff.

12.3.1. Study location

The study will be located in NYC.

12.4. Total number of study sites/total number of subjects projected

There is one study performance site (NYU). NYU manages field site spaces. The address of the NYU field site is NYU, [name].

A total of 48 participants (estimated minimum) will be enrolled in the refinement phase.

A total of 448 participants will be enrolled in the optimization trial.

Peers will be assessed as part of Component C (N=672) in the optimization trial.

12.4.1. Duration of study participation

Participants will be enrolled in the study for 12 weeks.

12.5. Study population

Adult Black and Latino/Hispanic frontline essential workers (FEW) in lower status occupations

The occupations of interest are:

- food preparation and serving (e.g., deli, bodega, restaurants, fast food)
- retail and sales (e.g., grocery, drug, and convenience stores and other kinds of stores)
- building and grounds cleaning and maintenance (e.g., janitorial services, security, reception, landscaping)
- building and home construction (including carpentry)
- personal care and service (e.g., in-home childcare workers, barbers, nail technicians, cosmetologists)
- in-home health care services (e.g., home health aides)

Retail work is any type of employment that involves customer interaction and sales. Includes:

- Sales associates are responsible for assisting customers as they look for products, keeping the store clean, ensuring the shelves are well-stocked and occasionally helping customers check out.

- Cashiers are responsible for checking customers out at the point of sale, helping customers return or exchange items and answering telephone calls at the sales desk area.
- Inventory associates are responsible for managing inventory, recording the details of shipments and sales and stocking particular items in the warehouse or front of the house.
- Customer service representatives manage online or phone-based customer comments, questions and concerns, resolve issues with customers and document customer interactions.
- Warehouse clerks receive and manage goods and products, package and send orders to customers, maintain stock organization and track all products in the warehouse.
- Assistant store managers maintain the employee work schedule, handle day-to-day store oversight, manage customer concerns and assist the store manager as needed.
- And other job titles

12.5.1. Eligibility criteria for the optimization trial and definitions where needed (REVISED MAY 2, 2023)

- 1) age 18-70 years
- 2) can engage in study activities in English or Spanish
- 3) Black or African American (including Caribbean, African, or multi-ethnic Black) and/or Latino or Hispanic race/ethnicity
- 4) resides in NYC
- 5) in the past month, was employed as a frontline worker in a frontline essential occupation in one or more of the domains listed above
- 6) has a phone that can be used for study participation and can receive text messages
- 7) has not received any dose of a vaccine for COVID-19 (including booster doses) in the past 12 months (FORMERLY: is not “fully vaccinated” for COVID-19; see below for definition)
- 8) has not been tested for COVID-19 in the past three months (FORMERLY: has not been tested for COVID-19 in the past six months)
- 9) if previously diagnosed with COVID-19, has not been symptomatic in the past two weeks or 90 days has passed since treatment with monoclonal antibodies or convalescent plasma⁹⁸
- 10) has not been educated/interviewed as a peer for Component C
- 11) willing to engage in a core session and be randomly assigned to receive 1-4 components
- 12) not a member of the study’s Community Advisory Board
- 13) was not enrolled in the study’s refinement phase (the pilot study)

Activities will be carried out in English and Spanish.

Consistent with the NYC DOHMH, we define “fully vaccinated” as: People who have received either both doses of the Pfizer or Moderna primary vaccine series or the one dose of the Johnson & Johnson/Janssen primary vaccine series (<https://www1.nyc.gov/site/doh/covid/covid-19-data-glossary.page>).

Participants who do not meet all of the eligibility criteria will not be enrolled. Any violations of these criteria will be reported in accordance with UCAIHS Policies and Procedures.

13. Study Procedures for the optimization trial

13.1. Participant identification number

The participant identification number used on all forms will be comprised of

- First two letters of first name
- First two letters of last name
- Birth date (MM/DD/YY)

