15.5.3. Data integration

Integration of qualitative and quantitative results will follow procedures outlined by Fetter and colleagues (2013) and use the joint display method¹⁸². A joint display is a state-of-the-art visual tool (i.e., a side-by-side visual presentation of results) to integrate data sources. The process brings about new insights beyond the information gained from the separate quantitative and qualitative results. Drs. [name] will lead the effort to integrate data with the interpretive community (including CAB). This will be an iterative process in which each joint display table reveals insights about the merged findings that shape subsequent iterations. Thus, joint displays are both a method and a cognitive framework for data integration and facilitate the production of new inferences¹⁸². We are experienced with data integration and joint display methods¹⁸³⁻¹⁸⁵.

All data provided to the CAB will be de-identified.

16. Safety Management & Study Administration

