16.1.2. Protection of confidentiality in REDCap

Participants will be identified by their Participant Identification Number in the REDCap database. A separate form linking participants’ names with the Participant Identification Number will also be included in REDCap. All consent forms will be signed in REDCap (the eConsent feature) and all assessments will be conducted in REDCap. Documentary evidence of COVID tests results will also be entered into REDCap. REDCap was designed specifically to protect patient and research participant

privacy and confidentiality while assisting investigators in conducting clinical research. The REDCap database can be shared among NYU authorized staff.

We will use computer-assisted personal interviewing (CAPI) and audio computer-assisted self-interviewing (ACASI) for sensitive sections of the assessments. In ACASI the respondent listens to digitally recorded questions and response categories through headphones, and enters her/his answers by using the computer keyboard or touching the computer screen. We have used ACASI with participants in past studies and found that participants were comfortable with using computers and appreciated the privacy it afforded. At each assessment period, the participant can opt out of the entire assessment or any part of the assessment.

Audio-recordings and transcripts will be stored on NYU's cloud-based and password-protected application, NYU Box. Recordings will be professionally transcribed within six months of collection and audio-recordings will be deleted within six months of transcription. Transcriptions will not include identifying information and are labeled with the participant's identification number.

Participant safety will be monitored by query regarding adverse events at all contacts and social harms in domains such as occupation, health care, and housing will be assessed at FU assessments.

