16.3. Data sharing with RADx-Up

The study will obtain permission from participants to collect and share de-identified data with the NIH RADx -UP Coordination and Data Collection Center (CDCC) and RADx Data Hub using specific language in the Informed Consent Forms (ICF).

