16.4.2. Confidentiality safeguards

All participants receive a participant identification number (PIN). This number will be used for all materials, audio-recordings, transcripts, study visit notes, and assessments. No other information that would disclose the participant's identity will be found on any assessments, notes, audio files, or in the transcripts of qualitative interviews.

Study staff do not collect paper forms; all materials are located in the secure REDCap database. Participants provide signed consent electronically and the signature is recoded in REDCap. Staff receives training about confidentiality. Participants will be provided a paper copy of the consent form that includes contact information for the research team PI and the IRB as appropriate. Participants can use this contact information to report adverse events or unanticipated problems.

Names and other identifying information will be redacted from transcripts.

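### The participant ID is built from name letters and the full birth date, which contradicts the statement that transcripts labelled with it carry no identifying information; the plan does not say the ID is recoded before sharing

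*Combined protocol and SAP*

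**What the plan says.** All references are to the combined protocol and SAP.

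- **13.1**: "The participant identification number used on all forms will be comprised of" three elements: "First two letters of first name", "First two letters of last name" and "Birth date (MM/DD/YY").
- **16.4.2**, on the ID: "This number will be used for all materials, audio-recordings, transcripts, study visit notes, and assessments". It adds that nothing else on those items would reveal who the participant is, and that names and other identifiers are redacted from transcripts.
- **16.4.1** identifies participants by the same number in REDCap and says computerized files outside REDCap carry only that label.
- **16.1.2**: "Transcriptions will not include identifying information and are labeled with" the participant's ID. It also describes a separate form that links names to IDs.
- **15.4** sets the data security level for transfer to the RADx-UP coordinating center (CDCC) at LIMITED. It withholds names, street address, telephone and fax numbers, email, medical record numbers and health plan numbers, and sends all other data. Neither birth date nor the participant ID is on the withheld list.
- **16.3** says the study will obtain permission to "collect and share de-identified data with the NIH" center and data hub.
- **15.5.3**, on the community advisory board (CAB): "All data provided to the CAB will be de-identified".

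**The concern.** A separate linking form makes sense only if the ID is a neutral code that means nothing without the form. An ID made of name letters and a birth date is not neutral: anyone who already knows those facts about a participant can construct the label and look for it.

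Loss of confidentiality is the first risk the protocol names (16.14.1). Section 4.1.1 lists unemployment, eviction and deportation among the feared consequences of a positive test. Component A sessions are audio-recorded and address fears that include immigration status (section 5), and Table 4 includes immigration status in the assessment battery. Audio goes to professional transcription (16.1.2). Transcripts are analysed in Dedoose and interpreted by a group that includes the community partner organization (15.5.2). Labelled material is therefore not confined to REDCap, and the point stands even if no quantitative export carries the ID.

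**Working it through.** The plan gives no figure to reproduce. The check sets sections side by side, with a short illustration of how distinctive the ID is.

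**1. Definition against confidentiality statement.** Section 13.1 puts name letters and a full birth date into the ID, and 16.4.2 puts the ID on transcripts. Section 16.1.2 says transcripts bearing the ID hold no identifying information. These three statements are inconsistent. Section 16.4.2 also redacts names from the body of a transcript whose label contains letters of the name. Its assurance covers only information other than the ID, so read literally it is compatible with an identifying ID; 16.1.2 is not.

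**2. Sharing.** Section 15.4 works by exclusion: what is not listed is sent. The ID and birth date are not listed. Section 16.4.1 mentions that REDCap has de-identification functions for export, but does not say they will be applied or that they would remove or recode the ID. No section provides for recoding. Separately, 15.4 (LIMITED) and 16.3 (de-identified) describe the transfer to the same center in different terms.

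**3. How distinctive the ID is (illustration).** Inputs: ages 18 to 70 (12.5.1) and N = 448 (12.4). Assumptions not in the documents: birth dates evenly spread; 500 to 10,000 effective combinations of the four letters; reference populations of 1 and 5 million adults of these ages.

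- Possible birth dates: 53 × 365.25 = 19,358. The span is under 100 years, so a two-digit year is unambiguous.
- Birth date alone, no match among the other 447 participants: (1 − 1/19,358)^447 = 0.977.
- Full ID: 19,358 × 500 = 9.68 million cells, up to 19,358 × 10,000 = 193.6 million. Unique within the trial: (1 − 1/9.68 million)^447 = 0.99995 or higher.
- Full ID in a population of M, where expected others sharing it = M/cells and P(unique) = (1 − 1/cells)^(M − 1):

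| M | Expected others sharing the ID | P(unique) |
|---|---|---|
| 1 million | 0.10 to 0.005 | 90% to 99.5% |
| 5 million | 0.52 to 0.03 | 60% to 97% |

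**4. Whether the ID needs these elements.** Date of birth is a separate screening item (13.2), and the repeat-enrollment check in 13.6 uses date of birth and name directly. A neutral ID loses nothing there.

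**The case against.** The case on the other side is substantial.

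- **Access is restricted.** Section 16.4.1 limits REDCap to study staff, requires double passwords for files outside it and limits the audio store to project staff. Section 16.4.4 adds a Certificate of Confidentiality. These controls limit who can see a label. They do not reconcile 13.1 with 16.1.2.
- **The ID is not a name.** Two letters of each name plus a birth date do not tell a stranger who the person is. The linking form still protects against a reader with no outside knowledge. This stands: the ID is an identifying code derived from name and birth date, not a direct identifier.
- **Much of the material is identifiable anyway.** REDCap openly holds identifiable information (16.1.1), and recordings carry the participant's voice and are deleted within months. This also stands, so the added exposure lies mainly in transcripts and in any shared dataset.

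Two stronger readings are tempting. A reader might infer that every export to the CDCC or the CAB carries the ID. No section says so: for the CDCC it is an inference from the withheld list in 15.4, and 15.5.3 commits to de-identified data for the CAB. A reader might also infer that a CAB member or an employer could look up a participant's transcript or test results. That presumes possession of labelled files, and the plan gives an employer no route to them.

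**Conclusion.** The contradiction between 13.1 and 16.4.2 on one side and 16.1.2 on the other is in the text and needs no assumption. The gap on sharing is also textual: the plan does not say that the ID is removed or recoded, and 15.4 and 16.3 do not agree on what kind of data are transferred.

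As to size, all 448 participants carry such an ID. Under the stated assumptions it is close to unique to one person, but these percentages are not breach probabilities. They describe what someone could do who already holds a labelled file and knows the participant's name and birth date. The point does not touch the outcome, randomization, sample size, power or primary analysis. It should be corrected because it bears on a stated risk and the remedy is simple, but it ranks below must-fix.

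**What to change.** 1. In 13.1, make the ID a random or sequential REDCap number not derived from personal data.
2. Keep name and birth date only in the restricted linking and screening records, where they still serve the duplicate check in 13.6.
3. Relabel retained transcripts and audio, and any shared files that carry the old code, through a checked one-time crosswalk. This is worthwhile even if data collection has ended.
4. State in 15.4, 15.5.3 and 16.3 that any code derived from name or birth date is excluded from CDCC and CAB files.
5. Reconcile 15.4 (LIMITED) with 16.3 (de-identified), and say whether birth date itself is transferred.

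The cost is an IRB modification and the relabelling. Re-keying touches baseline, two follow-ups and component records, and possibly data already sent to the CDCC, so the crosswalk must be checked for linkage errors before the old code is retired.
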